13.5. Efficacy Analyses

Efficacy analyses will be conducted using the FAS population.

13.5.1. Primary Efficacy Analysis

The primary endpoint will be analyzed using the Cochran-Mantel-Haenszel (CMH) test adjusted by randomization stratification factor (study site) to assess the treatment difference in the proportion of responders in the FAS. Estimate of treatment difference, p-value, and the 2-sided 95 % confidence interval will be calculated.

If a subject withdraws from study, the subject will be counted as a non-responder at time points after study withdrawal. The subject will also be considered a non-responder at the time point when data are missing. All observed data will be used for primary analysis.

Sensitivity analyses utilizing alternative methods for handling missing data will be performed to assess the robustness of the primary analysis result. Alternative methods may include complete case analysis (observed value analysis). Details will be specified in the statistical analysis plan (SAP).

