13.1. Statistical Hypothesis

The primary efficacy endpoint is the proportion of subjects who tolerate a cumulative dose of at least 2040 mg milk protein during a DBPCFC at week 18. The comparison between the dupilumab plus milk OIT arm (Cohort A) and the placebo plus milk OIT (Cohort B) arm will be made.

Letting p_D (and p_P) be the true proportion of subjects who tolerate a cumulative dose of at least 2040 mg milk protein during a DBPCFC at week 18 in the treatment arms of dupilumab + milk OIT and placebo + milk OIT, respectively. The following hypothesis for the superiority testing will be tested at the 5% 2-sided significance level:

$H_0: p_D = p_P$, i.e. the proportion of subjects who tolerate a cumulative dose of at least 2040 mg milk protein during a DBPCFC at week 18 is the same between dupilumab + OIT arm and the placebo + OIT arm

against the alternative

$H_a: p_D \neq p_P$, i.e. the proportion of subjects who tolerate a cumulative dose of at least 2040 mg milk protein during a DBPCFC at week 18 are different between the dupilumab + OIT arm and the placebo + OIT arm

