13.2. Justification of Sample Size

It is assumed that the proportion of subjects who tolerate a cumulative dose of at least 2040 mg milk protein during a DBPCFC at week 18 will be 20%, based on prior data, with the proportion of patients in the dupilumab + OIT arm assumed to be 55%, which is considered to be a clinically meaningful benefit by adding on dupilumab treatment. A sample size of approximately 88 subjects (44 in dupilumab + OIT and 44 in placebo + OIT) will have 90% power to detect the treatment difference of 35% between placebo + OIT and dupilumab + OIT at the 2-sided 5% significance level. Assuming a 25% drop out rate, we will enroll 58 in each arm. The sample size calculations were done by Fisher exact test using SAS (version 9.4, Cary, NC).

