13.8. Interim Analyses

Interim analyses to investigate the primary efficacy endpoint are planned after the first 40 participants (20 per arm) are enrolled and complete their Week 18 DBPCFCs. The interim analysis is designed to allow for early stopping when we reject the null hypothesis with a significant difference in the proportions of participants who tolerate a cumulative dose of at least 2040 mg

milk protein during the Week 18 DBPCFCs between the two treatment arms. The O'Brien-Fleming decision boundary is used to control the overall type I error probability at the conventional 0.05 level. The Lan-DeMets error-spending approach that approximates O'Brien-Fleming is used to determine the alpha with the information fraction of 45.5% (40 out of 88 participants). At the interim analysis stage, the null hypothesis will be rejected if the test is significant at the alpha level of 0.002 with an associated absolute Z statistic of 3.13. Thus, the trial will be stopped if the test statistic is less than or equal to -3.13 or greater than or equal to 3.13 with a p value ≤ 0.002 ; otherwise, the null hypothesis will be accepted and the trial will be continued.

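### The plan has no rule for reporting the effect after an early efficacy stop; at 20 per arm the ordinary difference would then average about 55 points against a true 35

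*Combined protocol and SAP*

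**What the plan says.** Section 13.8 places one look after the first 40 participants, 20 per arm, have completed their week 18 challenges. The boundary is O'Brien-Fleming with Lan-DeMets spending, and "the trial will be stopped if the test statistic is less than or equal to -3.13 or greater than or equal to 3.13". The nominal level at that look is 0.002.

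Section 13.5.1 names the site-stratified Cochran-Mantel-Haenszel (CMH) test on the full analysis set and then says: "Estimate of treatment difference, p-value, and the 2-sided 95 % confidence interval will be calculated". It names no interval method and does not mention the interim look. It counts withdrawn or missing subjects as non-responders, and 13.3.1 defines the full analysis set as everyone randomized.

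The only text on stopping early is a convention in 13.7 about which parameters are summarized after premature termination, plus 15.5, under which therapy is not continued if the study is discontinued. Neither says how the treatment effect is estimated. The opening of section 13 says the final SAP will be issued before the database is locked and unblinded.

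**The concern.** A trial that can stop only on an extreme early result will, when it stops, usually have stopped on a result more extreme than the truth. The O'Brien-Fleming boundary controls the type I error of the test. It does nothing for the estimate or the interval reported after the stop.

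If 13.5.1 is applied as written after a crossing, the ordinary difference from about 40 people becomes the trial's main result and the natural planning figure for the next study. A later trial sized on 55 points when the truth is 35 would be underpowered. A rule chosen after a crossing has been seen would not be prespecified.

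**Working it through.** **Inputs.** Two-sided 5% (13.1); placebo rate "will be 20%, based on prior data" and dupilumab rate 55%, a 35-point difference (13.2); "A sample size of approximately 88 subjects (44 in dupilumab + OIT and 44 in placebo + OIT") (13.2); look at 20 per arm and boundary 3.13 (13.8); CMH test (13.5.1). Assumed, because the plan is silent: exactly 20 per arm at the look, no dropouts, no overrun, one stratum.

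**The plan's own figures.** Exact enumeration of the Fisher test at 44 per arm, 55% vs 20%, gives power 90.8% (stated 90%). Information fraction: 40/88 = 0.4545. Spending: 4 × [1 − Φ(z(0.9875)/√0.4545)] = 0.00177, and z(1 − 0.00177/2) = 3.126. Both match the stated 0.002 and 3.13.

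**Stopping rule at 20 per arm.** With x and y responders, d = x/20 − y/20 and p = (x + y)/40, the pooled statistic is d/√[p(1 − p) × 2/20]. The single-stratum CMH statistic is that times √(39/40).
- 10/20 vs 1/20: d = 0.45, p = 0.275, pooled Z = 0.45/0.1412 = 3.19, CMH Z = 3.15. Both cross.
- 8/20 vs 0/20: d = 0.40, p = 0.20, pooled Z = 0.40/0.1265 = 3.16 (crosses), CMH Z = 3.12 (does not).

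The smallest positive difference that can stop the trial is therefore 45 points with CMH and 40 with pooled Z.

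**Given a stop.** All 21 × 21 outcomes were weighted by their binomial probabilities and kept if CMH |Z| ≥ 3.13. Wald is d ± 1.96 SE and the repeated interval is d ± 3.13 SE, with SE = √[p1(1 − p1)/20 + p2(1 − p2)/20].

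| True rates | P(stop) | Mean d given stop | Wald | Newcombe | Repeated CI |
|---|---|---|---|---|---|
| 55% vs 20% (35 points) | 19.6% | 54.7 | 72.7% | 90.1% | 96.1% |
| 45% vs 20% (25 points) | 6.5% | 52.1 | 49.2% | 69.2% | 93.9% |

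Practically all Wald misses lie above the true difference.

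**Sensitivity to the test statistic (55% vs 20%).** Pooled Z: bias +19.5, Wald coverage 73.6%. Unpooled Z: +16, 83%. Fisher at 0.002: +23, 56%. Continuity-corrected Z: +24, 51%. Simulated site-stratified CMH with 2 or 3 sites (split assumed): +20.2 to +20.7, 67% to 71%.

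**Whole design (stop at 20 per arm or continue to 44 per arm).** If the trial continues, the estimate averages 32.8 points and Wald coverage is 96.5%.
- Mean estimate: 0.196 × 54.7 + 0.804 × 32.8 = 37.1, a bias of about +2 points.
- Wald coverage: 0.196 × 72.7% + 0.804 × 96.5% = 91.8%. A fixed 44-per-arm trial gives 94.5%.
- With the repeated interval after a stop: 0.196 × 96.1% + 0.804 × 96.5% = 96.4%.

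**What the repeated interval costs.** Take 13/20 vs 2/20: d = 55 points, SE = √(0.011375 + 0.0045) = 12.6 points. Wald runs from 30.3 to 79.7 and the repeated interval from 15.6 to 94.4.

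**The case against.** **The interval is not named.** A reader might take 73% as a property of the plan. It is a Wald figure. Newcombe covers 90% given a stop at the design effect, and Wald falls short at 20 per arm even without stopping (92.0%, against 94.7% for Newcombe). This stands. A better interval does not remove the problem, though: Newcombe falls to 69% at 45% vs 20%, and the choice of interval leaves the bias untouched.

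**The estimate after a stop may not be the 40-participant estimate.** A reader might infer that every early stop must report at least 10 points more than the planned 35. The documents do not support that. It needs CMH Z on exactly 20 per arm; pooled Z can cross at 40 points. It also needs the 13.5.1 estimate to rest on the 40 completers, whereas 13.5.1 uses all randomized subjects. At the 25% dropout assumed in 13.2, 40 completers correspond to 40/0.75, about 53 randomized. If dropouts count as non-responders, 54.7 becomes 54.7 × 0.75 = 41 and a 45-point crossing becomes 34. If instead there are no dropouts but 10 more per arm are still short of week 18, the figure is 54.7 × 20/30, about 36, if they count as non-responders, or (54.7 × 20 + 35 × 10)/30, about 48, if they reach week 18 at the assumed rates. The plan does not settle which applies.

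**The large figures are conditional on a one-in-five event.** This is true, and the whole-design bias is small. But once the trial has stopped, the conditional result is the one that will be read.

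**Accepted methods differ.** Stage-wise-ordered intervals equal the ordinary interval at a first look, so preferring the repeated interval is a choice. It is made here for its coverage after a stop.

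**The final SAP is still to come.** This makes the change easy, but no current text supplies the rule.

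**Conclusion.** The point holds as a reporting gap. Applied as written after an early stop, 13.5.1 gives an estimate biased in the favourable direction and an interval that covers too seldom. At 55% vs 20%, 20 per arm, with no dropouts or overrun, the bias given a stop is about +20 points, and coverage is about 73% (Wald) or 90% (Newcombe). The chance of being in that position is about 20%. Over the whole design the bias is about +2 points and Wald coverage about 92%, against 94.5% for a fixed trial.

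That the ordinary estimate would be used after a stop is inferred from the absence of any other rule. It would be wrong to conclude that the interim test is invalid: the boundary reproduces and type I error control at the look is not in question. It would also be wrong to say that the trial as a whole overstates the effect by 20 points.

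**What to change.** Before the interim look, add to 13.5.1 and 13.8:

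1. If the trial stops early, the reported interval is the repeated confidence interval at the interim critical value, the difference ± 3.13 SE. In Wald form it covers 96% given a stop and 96% overall at 55% vs 20%.
2. Whether the estimate after a stop uses the 40 completers or all randomized subjects, and how subjects not yet at week 18 are counted.
3. A further estimate that includes participants who reach week 18 after the cut-off.

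A bias-adjusted estimate, such as Whitehead's, may be shown beside the observed one, with a note on its limits. It corrects the unconditional bias: solving for the true difference whose whole-design mean is 54.7, with placebo rates of 10% to 20%, gives about 52. That removes only about 3 of the 20 points.

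The cost is a few lines of SAP text and code. The downside is a wider, less favourable interval after an early stop, by a factor of 3.13/1.96 = 1.6.

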13.5.2. Secondary Efficacy Analysis

Change in the cumulative tolerated dose of milk protein during a DBPCFC from baseline at week 18 and separately week 24 will be analyzed using analysis of covariance (ANCOVA) with treatment as the main effect, stratification variable (study site) and baseline tolerated cumulative amount of milk protein DBPCFC as covariates. In addition, a non-parametric analysis using the Van Elteren test will be conducted to assess the sensitivity to the assumption about normality of response variable as required by ANCOVA.

No imputation will be applied for the missing data for continuous endpoints at week 18, while every effort will be made to reduce the number of missing values. Sensitivity analysis using last observation carried forward (LOCF) will be conducted to assess the robustness of the result, with regard to handling of missing data. Other sensitivity analyses may be conducted and will be specified in the SAP.

For continuous endpoints at week 18 or week 24, the LOCF will be used to impute missing values from subjects who do not achieve 1000 mg daily milk protein at week 24 or early discontinued from study before week 24. No imputation will be applied for the missing data from other subjects.

All secondary endpoints will be analyzed descriptively at given visits. These descriptive analyses may include statistical tests depending on the type of data in the same way as described above.

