3.6.1. Blinding

Placebo control and randomization will be the main methods to minimize bias in this trial. DBPCFCs will be performed during screening, at week 18 and at week 24. During the DBPCFC, the order of the milk and placebo (oat) challenges will be chosen at random by the unblinded pharmacy personnel, and both the patient and study staff will be blinded to the randomized order of the challenges. Milk powder and its placebo (oat) are both off-white, dry powders and should be difficult to differentiate unless directly compared side by side. An unblinded pharmacist or dietitian designee will mix the milk protein or oat in a food vehicle selected to aid in masking the taste and appearance of the food challenge doses prior to their dispensation for administration in the DBPCFC. To the extent practicable, the same blinded evaluating clinician who determines dose limiting symptoms in the screening DBPCFCs for a participant should evaluate the symptoms in week 18 and 24 DBPCFCs.

Dupilumab and placebo matching dupilumab will be labeled for research purposes in such a way that maintains the blind. Both the active product and placebo are identical in appearance.

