13. STATISTICAL ANALYSIS PLAN

This section provides the basis for the statistical analysis plan (SAP) for the study. The SAP may be revised during the study to accommodate amendments to the clinical study protocol and to make changes to adapt to unexpected issues in study execution and data that may affect the planned analyses. The final SAP will be issued before the database is locked and unblinded.

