13.5.4. Multiplicity Considerations

The overall Type-1 error rate of 0.05 (2-sided) will be controlled for the primary endpoint and the first secondary endpoint (ie, change in the cumulative tolerated dose [log transformed] of milk protein during a DBPCFC from baseline to week 18) using a hierarchical testing procedure. Inferential conclusions about the first secondary endpoint require statistical significance at the 2-sided 0.05 significance level of the primary endpoint.

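### Section 13.5.2 gives two conflicting missing-data rules for the type-I-error-controlled week-18 change in log CTD

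*Combined protocol and SAP*

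**What the plan says.** Section 13.5.2 analyses change in CTD by ANCOVA, with a Van Elteren test alongside. Its second paragraph deals with missing week-18 values: "No imputation will be applied for the missing data for continuous endpoints at week 18". It then gives LOCF a supporting role: "Sensitivity analysis using last observation carried forward (LOCF) will be conducted to assess the robustness of the result".

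The third paragraph reads: "For continuous endpoints at week 18 or week 24, the LOCF will be used to impute missing values from subjects". Two groups of participants are meant, namely those "who do not achieve 1000 mg daily milk protein at week 24 or early discontinued from study before week 24". It closes with its own statement that other subjects' missing values are not imputed. It is not labelled a sensitivity analysis, and it is the only missing-data rule given for continuous endpoints at week 24.

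Section 13.5.4 says that the overall 0.05 two-sided error rate "will be controlled for the primary endpoint and the first secondary endpoint", which it identifies as the week-18 change in log CTD, tested only if the primary endpoint is significant. Section 3.6.1 fixes when CTD is measured: "DBPCFCs will be performed during screening, at week 18 and at week 24". Section 13.2 plans for substantial loss: "Assuming a 25% drop out rate, we will enroll 58 in each arm". Section 13.3.1 bases efficacy on all randomized subjects.

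**The concern.** The two paragraphs give different instructions for the same people on the one secondary endpoint that carries a formal claim. Anyone who leaves before the week-18 challenge has a missing week-18 CTD, so the second paragraph leaves them out of the ANCOVA. They have also left before week 24, so the third paragraph keeps them in with a carried-forward value. No order of precedence is stated, so the main analysis cannot be run without choosing between the paragraphs.

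The third paragraph has a second problem. It decides whether a week-18 value is imputed partly from dosing status at week 24, six weeks after the endpoint.

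At stake are the estimate, its population and possibly the significance verdict. The primary endpoint is outside this, because section 13.5.1 counts missing as non-response.

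**Working it through.** **1. Inputs.** From section 13.2: 20% and 55% tolerating 2040 mg, 44 per arm evaluable, 25% dropout, 58 per arm enrolled. From section 3.6.1: challenges at screening, week 18 and week 24. From Table 1 and the schedule of events: the up-dosing ladder and visits. The documents give no mean or SD for log CTD.

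**2. The plan's own figure.** Exact enumeration of Fisher's test (two-sided 0.05, 20% vs 55%) gives power 0.908 at 44 per arm, so the stated 90% is reproduced. Inflating for dropout, 44 / 0.75 = 58.7, against 58 stated; the gap is rounding. No figure is given for the log-CTD endpoint.

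**3. Who falls under which rule at week 18.**

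| Participant | Second paragraph | Third paragraph |
|---|---|---|
| Leaves before the week-18 challenge | not imputed | LOCF |
| Stays, misses week 18, not at 1000 mg at week 24 | not imputed | LOCF |
| Stays, misses week 18, at 1000 mg at week 24 | not imputed | not imputed |
| Has a week-18 challenge, even if study drug was stopped | observed | observed |

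The first two rows are in conflict.

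**4. What LOCF means here.** The only challenge before week 18 is at screening. Carrying it forward gives change = 0.

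**5. The week-24 trigger.** Table 1 has 9 levels. Up-dosing can occur at Visits 5 to 10, 12 and 13, which is 8 visits (none at 11a or 14a). Starting at 5, 10 or 20 mg needs 8, 7 or 6 steps, leaving 0, 1 or 2 spare. For a 5 mg starter who stays on study but misses the week-18 challenge, one held step at any visit, including after week 18, decides whether the week-18 value is imputed.

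**6. Number affected.** 0.25 × 116 = 29 if all planned dropout precedes week 18; 0.10 × 116 = 11.6, about 12, if 10% does.

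**7. Effect on the estimate.** If dropout is random within arm, the expected difference with change = 0 is (1 − d_D) × Δ_D − (1 − d_P) × Δ_P, where d is the dropout share and Δ the mean change in each arm (D dupilumab, P placebo). Take assumed mean changes of 1.4 (dupilumab) and 1.0 (placebo) log10 units, so that no imputation gives 0.40:

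- 25% / 25%: 0.75 × 1.4 − 0.75 × 1.0 = 0.30
- 15% dupilumab / 35% placebo: 0.85 × 1.4 − 0.65 × 1.0 = 0.54
- 35% dupilumab / 15% placebo: 0.65 × 1.4 − 0.85 × 1.0 = 0.06

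**8. Effect on power (illustrative simulation).** 58 per arm; normal latent log10 threshold at week 18 calibrated to 55% and 20% reaching 2040 mg; assumed SD 0.5, 0.7 or 0.9; CTD read off the challenge ladder; assumed baseline CTD spread over 0 to 144 mg, correlation 0.3 with the week-18 threshold; log10(CTD + 1); dropout random within arm; ANCOVA on treatment and baseline, site omitted. Ranges cover repeated runs.

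| 25% dropout per arm | SD 0.5 | SD 0.7 | SD 0.9 |
|---|---|---|---|
| Power, no imputation | 99% | 99% | 99% |
| Power, change = 0 | 47–50% | 66–73% | 81–83% |
| Rules disagree on p < 0.05 | 49–53% | 27–33% | 17–19% |
| Disagree and primary significant | 43–44% | 23–25% | 11–12% |

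At 10% dropout per arm the rules disagree in 15–17%, 6–7% and 3% of trials.

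With unequal dropout, no imputation gives estimates of about 0.46 / 0.60 / 0.74. Change = 0 gives about 0.72 / 0.80 / 0.88 at 15% dupilumab / 35% placebo, and −0.02 / 0.11 / 0.24 at 35% / 15%.

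**The case against.** **The paragraphs can be reconciled.** The third paragraph might only detail the LOCF sensitivity analysis announced in the second, or it might be a specific exception to the second's general rule. Neither reading holds up well. The first leaves week 24 with no main rule and ignores that the paragraph is worded as a primary instruction. The second makes the LOCF sensitivity analysis largely redundant. The text does not choose between them.

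**Change = 0 is an inference.** The plan never says that a screening value may be carried into a treatment visit. If only post-baseline values may be carried, the two rules coincide for early leavers. That point is fair. But week 18 is the first post-baseline challenge, so on that reading the second paragraph's own week-18 LOCF analysis would have nothing to carry for anyone.

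**The sizes depend on assumptions.** This stands. Other assumed inputs (mean changes 1.0 and 1.4, SD 0.7) give 74% vs 50% power at 25% / 25%, with 30% disagreement. With 15% dupilumab / 35% placebo dropout, the direction the trial's hypothesis would suggest, the rules disagree on significance in only about 1% to 2% of trials, although the estimates differ. At 35% / 15% the primary itself succeeds in only about 63% to 66% of trials; when it does, the rules usually disagree.

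**The plan can still be finalised.** Section 13 says "The final SAP will be issued before the database is locked and unblinded". True, but the current text does not settle the rule. The interim in section 13.8 compares week-18 responder proportions by arm before lock. It tests only the primary endpoint, and nothing shows that those who finalise the plan would see its results, so settling the rule before then is prudence rather than a demonstrated need.

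**Complete-case sits oddly with intention-to-treat.** This also stands. It is a reason for the sponsor to choose deliberately, not for leaving both rules in place.

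**Conclusion.** The concern holds. Section 13.5.2 contains two incompatible main rules for missing week-18 CTD, and everyone who leaves before that challenge falls under both. This rests on the text alone.

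The practical size depends on how many week-18 values are missing, on the balance of dropout between arms, and on carrying the screening value forward. With none missing the rules agree. With 25% missing equally and unrelated to outcome, the zero-change rule shrinks the estimated difference by a quarter and can cost between about 16 and 52 percentage points of power over the assumed SDs. With unequal dropout it can move the estimate either way. The simulated figures are illustrative, since the documents supply neither SD nor mean for log CTD. The point should be fixed, but it does not touch the primary analysis or the sample size.

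**What to change.** Remove the reference to week 18 from the third paragraph of section 13.5.2, so that it governs week 24 only. The second paragraph then stands as the single week-18 rule: no imputation in the main analysis, with LOCF as the labelled sensitivity analysis. State that LOCF there means change = 0 for every randomized participant without a week-18 challenge. Apply the same missing-data rule to the ANCOVA and the Van Elteren test.

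If the sponsor prefers change = 0 as the main rule, to match non-responder handling of the primary endpoint, it should say so, make complete-case the sensitivity analysis, and accept the possible power loss and the dependence on dropout balance.

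Either choice is best fixed before the 40-participant interim. The cost is a few words in section 13.5.2 and in the final SAP, with no change to data collection. Keeping no imputation means that the main estimate describes only participants who had a week-18 challenge; choosing change = 0 is a change of estimand.

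Separately, the CTD definition assigns no value to someone who reacts to the first challenge dose. If that is scored as 0, the plan needs a log transform that keeps zeros, such as log(CTD + 1).

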During combination therapy, participants in **Cohort A** will continue to receive dupilumab, while those in **Cohort B** continue to receive placebo for dupilumab. Dupilumab/placebo doses will be administered at least 30 minutes prior to the in-clinic milk OIT dosing every two to four weeks. The last dose of dupilumab/placebo given in the study will be administered at week 16 (Visit 10).

Washout Phase (Visit 10 to Visit 14b, Weeks 16 to 24)

The final administration of dupilumab at week 16 will mark the beginning of the washout phase. Daily Milk OIT will be continued alone for 8 weeks, with DBPCFCs conducted at weeks 18 and 24.

Week 18 Double-Blind, Placebo-Controlled Food Challenge (Visits 11a and 11b)

At week 18, under clinician supervision, all subjects will return to clinic to undergo DBPCFCs up to 4040 mg milk protein (cumulative) and placebo to assess desensitization. The DBPCFCs will occur at two separate visits within the span of 7 days. Randomization of the placebo and milk challenge order and preparation of the challenge materials will be performed by trained unblinded study personnel. Both milk protein and oat will be concealed in an age-appropriate, non-offensive food vehicle to aid in masking the taste and appearance.

At Visit 11a, participants will return unused OIT doses remaining from the previously dispensed home dosing kit. Prior to the DBPCFC, accountability will be performed on the returned doses, when able, and the Daily Dosing & Symptom Diary will be reviewed to assess for AEs and home dosing compliance. Additionally, prior to the first dose of the Visit 11a DBPCFC, a blood draw will be performed.

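### LOCF for week-24 CTD carries a challenge done 2 weeks after the last injection into an endpoint 8 weeks after it, imputes selectively, and contradicts the non-responder rule for subjects who leave after week 18

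*Combined protocol and SAP*

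**What the plan says.** Section 13.5.2 analyses change in CTD by ANCOVA, separately at weeks 18 and 24. For continuous endpoints at either week it states that "the LOCF will be used to impute missing values from subjects who do not achieve 1000 mg daily milk protein at week 24", and the next clause adds "or early discontinued from study before week 24". Missing values from all other subjects stay missing. For week 24 this is the main method; further sensitivity analyses are optional.

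Section 13.5.1 treats the responder endpoint differently. After withdrawal, "the subject will be counted as a non-responder at time points after study withdrawal". For missing data in general, "The subject will also be considered a non-responder at the time point when data are missing". The rule is written for the primary endpoint, which has a single time point, but it speaks of time points in the plural. Section 13.5.2 then says of the secondary endpoints: "These descriptive analyses may include statistical tests depending on the type of data in the same way as described above". I read the non-responder rule as covering the week-24 thresholds in Section 3.5.2 (1040, 2040 and 4040 mg). That is by implication; it is not stated outright.

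On timing, Section 8.3 says "The final administration of dupilumab at week 16 will mark the beginning of the washout phase" and "Daily Milk OIT will be continued alone for 8 weeks, with DBPCFCs conducted at weeks 18 and 24". Footnote 14 of Table 4 omits injections for four-weekly participants only at Visits 3, 5, 7 and 9, so week 16 is the last injection on both schedules. Section 6.1.1.2 (18 weeks of dosing) and Section 1.2.2 (a maintenance period with concomitant dupilumab or placebo) do not fit this and must be reconciled with it. The intervals used here rest on Section 8.3.

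**The concern.** There are three separate problems.

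- **Persistence is assumed.** Week 24 is the only efficacy challenge well clear of the last injection. Filling it with the week-18 value supposes that nothing changes in between.
- **Imputation depends on outcome.** A subject still in the study at 1000 mg daily with a missing challenge is dropped. One still in the study below 1000 mg is filled in. Reaching 1000 mg happens after randomisation, and dupilumab is meant to influence it.
- **Two week-24 endpoints can disagree by rule.** CTD and the thresholds come from the same challenge, but a late leaver is handled in opposite ways.

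At stake is the credibility of the week-24 comparison: the continuous and responder results could diverge because of imputation alone.

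**Working it through.** The plan gives no figure for this point. The response rates and arm size borrowed below come from Section 13.2, and they reproduce: Fisher exact power for 20% against 55% with 44 per arm is 90.8% (stated 90%), and 44/0.75 = 58.7 per arm (stated 58).

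**Step 1: which value is carried.** Cumulative screening doses are 1, 4, 14, 44, 144 and 444 mg. A reaction at or before 444 mg is required for entry, so baseline CTD is at most 144 mg. Cumulative doses at weeks 18 and 24 are 10, 40, 140, 440, 1040, 2040 and 4040 mg.

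- Leaver before week 18: carries baseline, at most 144 mg. Change is zero and every threshold is failed. The two rules agree.
- Leaver after week 18: carries the week-18 CTD, taken at 18 − 16 = 2 weeks after the last injection, into an endpoint at 24 − 16 = 8 weeks. Both intervals are nominal, because visit windows are ±5 days and the second challenge may follow by up to 7 or 10 days.

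**Step 2: one subject under both rules.** A subject tolerates 4040 mg at week 18 and then leaves.

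- CTD by LOCF: 4040 mg, the maximum. The log10 change is log10(4040/144) = 1.45 from a 144 mg baseline, or log10(4040/14) = 2.46 from 14 mg.
- Thresholds: non-responder at 1040, 2040 and 4040 mg.
- Against scoring at baseline, this one subject moves the mean of a 58-subject arm by 1.45/58 = 0.025 to 2.46/58 = 0.042 log10 units.

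**Step 3: how many such subjects.** The documents do not divide the 25% dropout into before and after week 18. Assume that k of 58 per arm leave after week 18 independently of response, that week-18 rates at 2040 mg are 55% and 20%, and that stayers keep their status. Leavers counted as tolerating 2040 mg by LOCF but failed by the responder rule number k × 0.55 and k × 0.20. The difference at 2040 mg is 35 points under LOCF and 35 × (1 − k/58) under the non-responder rule.

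| k per arm | Conflicting, dupilumab / placebo | Difference, LOCF | Difference, non-responder rule |
|---|---|---|---|
| 3 | 1.7 / 0.6 | 35 points | 33.2 points |
| 6 | 3.3 / 1.2 | 35 points | 31.4 points |
| 14 | 7.7 / 2.8 | 35 points | 26.6 points |

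This measures disagreement between the rules, not bias.

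**Step 4: bias in the CTD ratio.** Let m be the share missing after week 18, equal in both arms, and let L be the natural-log fall in leavers between the carried value and their true week-24 value. Then bias in the log difference = m × (L for dupilumab − L for placebo).

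Assume m = 5% to 15% and dupilumab leavers falling from 2040 to 440 mg, so L = ln(2040/440) = 1.53.

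| Placebo leavers (assumption) | L placebo | Difference in L | Ratio at 5% | Ratio at 15% |
|---|---|---|---|---|
| No change | 0 | 1.53 | exp(0.077) = 1.08 | exp(0.230) = 1.26 |
| Fall from 440 to 140 mg | ln(440/140) = 1.15 | 0.39 | exp(0.019) = 1.02 | exp(0.058) = 1.06 |
| Same log fall as dupilumab | 1.53 | 0 | 1.00 | 1.00 |

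With no change over time in either arm the bias is also zero.

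**The case against.** The best defence is that LOCF does little harm here. Section 1.1 says that 20-30% of milk OIT patients cannot complete up-dosing, and Visit 4 treatment failures are early by definition. Early leavers carry baseline, which is conservative and agrees with the responder rule. Week-24 CTD is outside the hierarchy in Section 13.5.4, secondary endpoints are analysed descriptively, and Section 13 is only the basis for a final SAP. All of this stands. It limits the consequence but does not justify the rule for late leavers or the selection on 1000 mg.

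A reader might infer that LOCF must favour dupilumab, because dupilumab leavers lose effect off drug while placebo participants gain from up-dosing at Visits 12 and 13. Adding a placebo rise from 440 to 1040 mg, ln(1040/440) = 0.86, would bring the inflation to exp(0.05 × 2.39) = 1.13 up to exp(0.15 × 2.39) = 1.43. The documents do not support that reading. A subject who has left is no longer up-dosing. Section 8.3 continues up-dosing for everyone below 1000 mg in both arms. Section 1.1 reports tolerance lost within weeks of stopping daily milk, which would apply to placebo leavers too and partly cancel the error.

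Nor is every leaver scored as a full success: that holds only for someone who tolerated 4040 mg at week 18. Finally, the protocol describes the week-24 challenge as assessing desensitisation. That it can test persistence off drug follows from its timing and is not a stated aim.

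**Conclusion.** The point holds for week-24 CTD in subjects with a missing week-24 challenge. The text establishes the carry-over from 2 to 8 weeks after the last injection and the dependence of imputation on reaching 1000 mg. The conflict with the week-24 thresholds follows once the non-responder rule is read across by implication.

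The direction and size of the bias are not established. They depend on dropout after week 18 and on loss of tolerance in each arm, and the documents give neither. The 8-26%, 2-6% and 0% figures illustrate assumed scenarios and are not estimates. It would go too far to conclude that the trial's main result is compromised: the primary endpoint and the week-18 key secondary are unaffected by this route. The change is still worth making before database lock, because it is cheap and removes an avoidable contradiction between week-24 results.

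**What to change.** In Section 13.5.2, replace the week-24 rule with one that covers every missing week-24 CTD, whether or not 1000 mg was reached:

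- Subjects who withdrew or were treatment failures: score at baseline CTD (zero change), to match the non-responder rule.
- Subjects still in the study with a missing challenge: multiple imputation from baseline and week-18 CTD, with arm and site in the model.
- Sensitivity analyses: LOCF as now written, and multiple imputation of all missing values. The latter should not be the main method, because it would give withdrawals and Visit 4 failures values modelled on completers and leave the conflict in place.

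State explicitly that the non-responder rule applies to the week-24 thresholds. A small mismatch remains for subjects still in the study with a missing challenge, whom that rule counts as failures; report their number by arm. In the same edit, settle the week-18 wording, where Section 13.5.2 gives both no imputation and LOCF.

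The cost is SAP wording and some programming, slightly wider intervals, and a week-24 effect that may look less favourable. Trial conduct does not change, and the opening of Section 13 allows SAP revision before lock.
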